| | Functional Impairment, Falls, and Fractures (4F) Fall Prevention |
| | Intervention Pilot Study |
| Population: | Up to 50 participants from the Boston ARCH 4F Study |
| Intervention: | The fall prevention intervention has 3 main components: home exercises, virtual group sessions and weekly phone check-ins. Home |
| | participants. Participants will be asked to complete assigned |
| | exercises 3 times per week. Additionally, there will be a weekly virtual group session led by an occupational therapist member of the study team trained in group facilitation via Zoom. The virtual group sessions will be used to help answer any questions and lead a discussion around challenges related to falls. Finally, a member of the research team will check-in with participants once per week to answer any remaining questions that participants have, provide individual feedback on exercises, and set up reminders for the upcoming week. Reminders will be tailored to the individual participant's needs to remind the participant to complete the intervention's components. |
| Objectives: | To examine the association between alcohol use and falls and fractures and whether frailty mediates these associations in people living with HIV (PLWH) |
| Design/Methodology: | The Fall Prevention Pilot will recruit participants from the Boston ARCH 4F Study to test the acceptability and feasibility of a randomized trial of a 10-week virtual intervention to reduce fall risk PLWH who consume alcohol. Eligible cohort participants with an elevated risk for falls will be randomized to either the intervention or control (usual care plus educational brochure). |
| Total Study Duration: | 1 year |
| Subject Participation Duration: | 10 weeks |

3 Background/Rationale & Purpose

3.1 Background Information

Up to a third of middle-aged people living with HIV infection (PLWH) experience falls each year.¹ Although not well-described in PLWH, falls are the most common cause of non-fatal injury in the US (8 million falls per year; 2.6 million treatment episodes; 750,000 hospitalizations, 22,000 deaths)^{2,3} and the cost in the elderly is enormous (\$20 billion/year), mostly from emergency department visits and hospitalizations (which have risen 50% in 7 years).² Falls are a common and significant problem in PLWH, and alcohol is a potent risk factor, increasing risk up to 17X.^{1,4–11} Alcohol, illicit drug use, and polypharmacy likely contribute to falls (e.g. from over-sedation and risk-taking behavior), risk factors for falls (e.g. frailty), and fall consequences (e.g. fracture, need for acute healthcare use). Interventions are needed to address falls in PLWH who use alcohol but none have been tailored for this population.

Efficacious interventions for the elderly exist^{12,13}; however, fall prevention interventions developed for the elderly generally do not address alcohol, other drugs, HIV medications, and HIV-associated comorbidity, but they would likely need to in order to be successful in PLWH. A focus on risks, including the interplay of common exposures (e.g. alcohol, illicit drugs, medications) and mediators (e.g. frailty), is therefore critical in order to develop tailored preventive interventions to reduce falls and related morbidity effective for PLWH.

3.2 Rationale and Purpose

Study Rationale:

Falls are a common and significant problem among PLWH for various reasons.^{1,4–11} Antiretroviral therapy (ART) can control HIV viremia even in substance use-affected populations. But HIV-associated comorbidity and complications, in the context of possible premature aging —or more accurately—the earlier development of comorbidities in PLWH seen in older adults without HIV infection, now contribute to substantial impairment in people with HIV infection. These complications, including Frailty and impaired physical Function, can contribute to Falls and Fractures, and can be hastened by alcohol, illicit drug use, and polypharmacy (5+ medications). Fall prevention interventions developed for the elderly generally do not address alcohol, other drugs, or HIV medications, but would likely need to in order to be successful in PLWH. A focus on risks, including the interplay of common exposures (e.g. alcohol, illicit drugs, medications) and mediators (e.g. frailty), is therefore critical in order to develop tailored preventive interventions to reduce falls and related morbidity effective for PLWH.

Purpose:

This study is being conducted to assess the acceptability and feasibility of conducting a randomized trial of a 10-week virtual intervention aimed at reducing fall risk in PLWH who consume alcohol. This pilot trial will be used to inform feasibility of this study design prior to conducting a large-scale trial. To achieve this, we propose to recruit up to 50 participants from the Boston ARCH 4F Study, 40 of whom

will be randomized, to pilot test this fall prevention intervention. Further, we will assess the acceptability and feasibility of the intervention component by assessing number of virtual group intervention sessions attended and administering the Client Satisfaction Questionnaire (CSQ-8)¹⁴ at the conclusion of the intervention.

- 4 Objectives
 - 4.1 Study Objectives

The primary aim of the intervention is to assess acceptability and feasibility of a randomized trial of a 10week virtual fall prevention intervention.

- 4.2 Study Outcome Measures
- 4.2.1 Primary Outcome Measures

To assess intervention acceptability and feasibility, the primary outcomes include number of weekly intervention sessions attended (out of 10 sessions) and overall satisfaction with the intervention [assessed at study conclusion using the Client Satisfaction Questionnaire (CSQ-8)].¹⁴

4.2.2 Secondary Outcome Measures

There are also several secondary outcome measures:

- Falls from participant self report, defined as an unexpected event, including a slip or a trip, in which a participant lost their balance and landed on the floor, ground, or lower level, or hit an object like a table or a chair.
- Physical Function measured using the Short Physical Performance Battery assessment
- Frailty phenotype¹⁵, which includes measures of exhaustion, low activity, weight loss, slowed walking, weak grip.
- Alcohol and other drug use from self report measured using the validated Addiction Severity Index (ASI)¹⁶⁻¹⁸
- 5 Study Design

The Boston ARCH 4F Fall Prevention Pilot is a sub-study of the Boston ARCH 4F Study, a longitudinal cohort study of 251 HIV infected men and women who have a spectrum of alcohol and other drug use. The Boston ARCH 4F study aim is to examine the association between alcohol use and falls and fractures and whether frailty mediates these associations in people living with HIV (PLWH). The Fall Prevention Pilot will recruit participants from the Boston ARCH 4F Study to test the acceptability and feasibility of a randomized trial of a 10-week virtual intervention to reduce fall risk PLWH who consume alcohol.

Eligible cohort participants with an elevated risk for falls will be randomized to either the intervention or control (usual care plus educational brochure).

Standardized assessments will be administered to all participants in-person at Boston University Medical Campus (BUMC) to assess various domains including fall risk, fear of falling, physical performance measures (such as grip strength, balance, and gait speed), substance use, and other related measures at baseline and at trial completion. The fall prevention intervention has 3 main components: home exercises, virtual group sessions and weekly phone check-ins. Home exercise will be customized to match the current fitness level of participants. Participants will be asked to complete assigned exercises 3 times per week. Additionally, there will be a weekly virtual group session led by an occupational therapist member of the study team trained in group facilitation via Zoom. The virtual group sessions will be used to help answer any questions and lead a discussion around challenges related to falls. Finally, a member of the research team will check-in with participants once per week to answer any remaining questions that participants have, provide individual feedback on exercises, and set up reminders for the upcoming week. Reminders will be tailored to the individual participant's needs to remind the participant to complete the intervention's components.

6 Potential Risks and Benefits

6.1 Risks

Potential risks for participants include psychological stress from the research interviews or from recognizing health disorders during the interviews or tests, loss of confidentiality, and social harms. These are minimal risks, consequences are not likely, and will be minimized further.

Psychological stress from research interviews or study visits: Participants may experience psychological stress from talking about their health or from recognizing health disorders during the assessments or intervention components. Participants may get tired during the visits. Additionally, participants may find it inconvenient to take time for the visits, and they may find it inconvenient to be contacted by study staff when they remind participants of an upcoming research visit. Participants will not be explicitly asked questions about self-harm and/or suicidal ideation as a part of this research study. However, if active/current suicidal ideations are identified via research assessment or expressed by participants during study visits, study physicians are available to respond to participant concerns with referrals as needed (remotely if during a remote visit or in-person if during an in-person interview). This process will be determined prior to the visit taking place, per recommendation of the staff facilitating the visit or phone call.

Discomfort from exercise assignments: Participants may experience muscle soreness, discomfort, and fatigue after completing the exercise assignments. There is the unlikely risk that a participant could get injured while doing the exercise assignments. However, all exercise assignments will be tailored to the individual's needs and skill levels, and study staff will make sure the participant has been provided with thorough instructions/demonstrations on how to properly do the exercises before they are instructed to proceed with doing the exercise assignments on their own. Participants are welcome to ask any questions during virtual group sessions or weekly phone check-ins.

Loss of confidentiality: Loss of confidentiality by someone seeing the responses to interview assessments is potentially the most serious risk of the proposed study, though it is very unlikely because specific procedures will be implemented to prevent such disclosure. In addition, much of the most sensitive information (HIV and alcohol use) is already in medical records and the additional increase in risk of

recording it for research purposes, particularly given the protections in place for such records that is far greater than clinical records, is small. There is a risk that participants may experience loss of confidentiality when research assistants make attempts to contact them for follow-up. All participants will be informed and provide their consent for the study to reach them through contacts they have provided as a part of the Boston ARCH 4F study (the participant will be linked to the Boston ARCH 4F study through their unique Study ID number). When research assistants attempt to make any contact to the participant or other contacts, all communications will be identified as coming from a "health study," not an alcohol abuse or HIV study. When study visits (such as group meetings or individual check-ins) are conducted via phone or confidential video conference, study staff will advise participants to take precautions to minimize the risk of a breach of confidentiality such as participants not to talk about the discussions outside the group, and research study staff will ask all participants not to talk about the discussions outside the group, and not repeat what is said in the group meetings to others. Participants will be asked to only provide their first name or a pseudonym.

How risks will be minimized.

Loss of confidentiality: To assure confidentiality, research data collection and data entry forms will be labeled only with the unique Boston ARCH 4F Study ID number, and will contain no other individual identification. Only the written informed consent forms, participant locator information, and a master list of participants and participant study identification numbers will have the participant number and identifying information on them. There will be only one master list of names and identification numbers. These data will be kept in a secure electronic environment accessible to the principal investigator, the study research staff and data managers. Study staff will use the tracking information that the participants provided during the Boston ARCH 4F study, and study staff will confirm that the tracking information is up to date and accurate. Computer data will be password protected, and accessible only to research assistants needing the information for follow-up purposes. When study visits (such as group meetings or individual check-ins) are conducted via phone or confidential video conference, study staff will advise participants to take precautions to minimize the risk of breach of confidentiality. Study staff will remind participants that they should participate in study activities in a private location. Participants will be provided the option to keep their camera off, if they would like. Prior to virtual group meetings, we will remind participants that they should not talk about the discussions outside the group. All of these procedures are likely to be effective, based on our experience with similar studies. Comments on the home exercise YouTube videos have been disabled to further protect participant confidentiality.

Psychological stress: The minimal risk of psychological distress from interviews and study visits will be minimized by using trained interviewers and a standardized interview process. To further minimize this risk, we will enroll participants who understand the study and are willing to participate. Participation is voluntary and participants can withdraw at any time. Additionally, we will take steps to mitigate the risk of psychological stress during the weekly virtual group sessions. The occupational therapist member of the research team is trained using Zoom to facilitate group sessions and will re-direct any inappropriate questions or topics. Each virtual group session will begin with a reminder of best practices and available resources. For example, we will remind participants that they are welcome to leave the group meeting at any time and follow up with a study team member if they experience psychological stress during the group session will be available by phone if undue stress arises, and they will be able to make recommendations or referrals as appropriate. Study team members will have a list of mental health and alcohol use resources that can be provided to participants who inform a study

team member that they are experiencing psychological distress as a result of the research study. Participants will also be reminded that phone check-ins can be used as an opportunity to discuss experiences of psychological distress, and participants are welcome to save sensitive or uncomfortable topics for discussion during the phone check in rather than the virtual group session.

Discomfort from exercise assignments: Participants will only be assigned exercises that have been tailored to their individual needs, skill level, and goals, which will be determined during the baseline assessment. The exercises and modifications will be demonstrated during the first virtual group session. We will ask that participants only perform the exercises exactly as instructed, and they should not do any exercises that make them feel uncomfortable (not including general muscle soreness or fatigue, which is a common and temporary risk). Video demonstrations of the exercises and modifications will be available on YouTube as "unlisted" videos that can be accessed only through a direct link that we will provide participants. Participants can refer to these demonstrations at any time. Participants will also be encouraged to discuss any discomforts that have resulted from exercise assignments with members of the research team during weekly virtual group meetings and phone check-ins.

Plans for ensuring necessary medical or professional intervention in the event of adverse effects to participants: If consequences arise due to research procedures (e.g., distress, anxiety, suicidal thoughts) the physician investigators will be available to assess participants and make appropriate interventions or referrals based on the clinical circumstances, immediately. This will be done either remotely or in person, whichever mode reflects the research activity being conducted. Three study physicians have extensive clinical experience with patients with substance use disorders and related mental health complications that arise, two have clinical expertise with HIV infection.

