Conflicts and Rescheduling: If a participant experiences a scheduling conflict with a scheduled group session, they will miss that visit. Study staff will inquire about the upcoming week during a participant's weekly phone check-ins. Participants who indicate that they will have a scheduling conflict with their assigned weekly virtual group session time will be offered participation in the other group for that week only. Further, if a participant experiences a scheduling change that causes them to be unavailable for

either of the 2 group sessions, the participant will miss the group meetings. However, the participant will to continue to participate in the intervention by attending the weekly phone check-ins and conducting the weekly exercise assignments, and participants will be encouraged to attend future virtual group meetings if they experience a schedule change that allows for their attendance. The weekly virtual group meeting sessions will be combined into one session if weekly participation drops below 3 participants per session for at least two consecutive weeks.

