The occupational therapist member of the study team will begin each group by reviewing the purpose and reminding participants that they can choose how much to share or not share. The purpose will be described as a forum to share their experiences with the intervention, discuss any falls during the week and identify strategies to address any challenges. The discussion will begin with a quick check in with each group member to provide a structured opportunity for every participant to speak at least once during the group. The check in will be a brief structured question such as, "Identify one exercise you liked doing this week and one that you might have had some difficulty with." This structure gives the participants permission to have challenges with the intervention to help alleviate discomfort or embarrassment with having to initiate this topic. It also ensures that every group member participates verbally should they be less active in the remainder of the discussion. Based on the check in responses, the occupational therapist member of the study team will facilitate a group discussion among participants that encourages them to share strategies and commonalities with each other. Group members find advice from peers to be more valid than from a professional. The occupational therapist member of the study team will use their expertise to ensure the conversation stays on the topic of falls and intervention strategies and to correct any misinformation that might be shared. The therapist will have a list of common topics to interject if the participants exhaust their own concerns or if the group conversation veers off course. Topics will include common issues related to fall prevention such as identifying and removing environmental obstacles, finding time to complete exercise, maintaining good nutrition to support physical health, and how to speak with your doctor about medication side effects such as dizziness, etc. Finally, group time may be spent reviewing exercises if needed. If individuals raise concerns that cannot be addressed in the group due to time or because the topic is beyond the scope of the group, they will be redirected to their individual session or another resource.

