Independent Home Exercises: Home based exercises will be tailored to each participant's individual needs and skill sets, which will be determined at the baseline assessment. The general categories of the exercises include air squats, bicep curls, burpees, and single leg stands. Links to the exercises can be found below. Participants will complete assigned exercises on their own at home and will be instructed to record the exercises they complete on the Home Exercise Form, which is a tool for personal use by the participant and will not be returned to the study team. The exercise assignments will take about 30 - 60 minutes to complete per time the participant exercises. During the first virtual group sessions, an occupational therapist member of the study team will describe and demonstrate the assigned exercises. Participants may use this time to ask questions about the exercises. Further, if a participant was unable to attend the first virtual group session, the assigned exercises will be demonstrated by an occupational therapist member of the study team during the first phone check-in. In the case that assigned exercises will be demonstrated at the first phone check-in, the phone check-in will occur using Zoom instead of phone call.

Participants will be able to refer back to video demonstrations of the assigned exercises on a YouTube channel called "Boston ARCH Home Exercises". The YouTube channel will include videos of occupational therapist members of the study team demonstrating the assigned exercises. The videos on the YouTube channel will remain at a visibility status of "unlisted", which means they can only be accessed by a URL. Comments on the videos have been disabled. Study staff will provide participants with the limited access URLs at the first virtual group session, phone check-in, or by email upon participant request. Participants will be encouraged to keep the limited access URLs private and not share the links with people outside of the study.

URLs:

https://youtu.be/BGR69rKSMCA https://youtu.be/mfrOBDuRP7M https://youtu.be/2IeSb2UXsm4 https://youtu.be/3ypbuWluf3M

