8.9 Individual Check-In via Phone Call

The phone check-in will occur between the first and second weekly virtual group sessions, and follow-up check-ins will occur once weekly after the initial check-in for the entirety of the intervention period, for a total of 10 weekly check-in calls. These phone calls will be conducted with an occupational therapist member of the study team. As the study's primary aim is to assess acceptability and feasibility, there is no set limit of missed weekly check-ins that triggers dropping participant from the study. If a participant stops participating in weekly exercises, the occupational therapist conducting the weekly check in with the participant will inquire as to the reasons why the participant stopped completing the exercises. This feedback will be used to modify the exercises going forward (e.g., frequency, intensity). Additionally, individualized reminders (e.g. phone alarm, calendar update) for the various intervention components will be set during the individual check-ins.

Post-Study Assessment- After the 10 week intervention is complete, all randomized participants (intervention and control groups) will be asked to complete a post-study interview (a series of questionnaires to assess fall history and efficacy, substance use, prescription medications, physical and social environment, food security, and frailty) and physical assessments (physical function measures including grip strength, short physical performance battery, and vision acuity) in-person at BUMC with an RA or RC. Additionally, an occupational therapist member of the research team will conduct the Canadian Occupational Performance Measure. The post-study assessment will take approximately 2 hours to complete. The RAs and RC will reach out to participants approximately 8-9 weeks after randomization to schedule the post-study assessment, and the post-study assessment will be completed approximately 10 weeks (up to 14 weeks) after randomization.

9 Informed Consent

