Consent will be sought by trained research staff under the supervision of the study investigators. Research study staff will have a conversation with the potential participant about the study, reviewing all pertinent elements of informed consent. If potential participants wish to review the information and consider their options they may do so and return to enroll at a later date if they remain eligible. Written consent will be documented. Consent will be obtained when potential participants arrive for their first research interview. Their clinical care will not be interrupted or interfered with. Research staff will review the elements of consent with participants (that this is a research study, description of the study procedures including that their study ID will link information from the Fall Prevention Pilot to the Boston ARCH 4F Study, that we will use contact information that was provided for the Boston ARCH 4F study, the risks and discomforts, the benefits, the alternative to participating in the study including to not participate in the research, the purpose and duration of the study, confidentiality, and that participation is voluntary). After research staff review the elements of consent with participants, they will use a "teachback" process among all participants to ensure participant comprehension. The study will begin immediately after informed consent by an RA.

10. Adverse Event Reporting

This study is not greater than minimal risk. Unanticipated Problems, Adverse Events, and protocol deviations will be reported to the IRB as required by IRB policies. The Principal Investigator at BU Medical Campus will report all adverse events and Unanticipated Problems to the IRB in compliance with IRB policy, Federal/State regulations, and sponsor requirements (as applicable).

11. Data Monitoring

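### No structured injury or adverse event question is specified in either arm, so exercise injuries may be missed and any adverse event counts would not be comparable between arms

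*Combined protocol and SAP*

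**What the plan says.** **The risk is acknowledged.** Section 6.1 states: "There is the unlikely risk that a participant could get injured while doing the exercise assignments". The exercises are done unsupervised at home, three times a week, for 30-60 minutes each time (sections 5 and 8.8). Participants are selected for fall risk and recent alcohol use (section 7.1).

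**How harm reaches staff.** Section 6.1 states: "Participants will also be encouraged to discuss any discomforts that have resulted from exercise assignments with members of the research team", at group sessions and check-in calls. In section 8.8 the group's purpose includes that members "discuss any falls during the week and identify strategies to address any challenges". Each session opens with a structured question, and the example given asks which exercise was liked and which was difficult. Under section 8.9, the therapist asks a participant who stops exercising for the reason.

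**Contacts can be missed.** Section 8.6 says of someone who cannot make either weekly slot that "the participant will miss the group meetings", while calls and exercises continue. Section 8.9 says that "there is no set limit of missed weekly check-ins that triggers dropping participant from the study". The home exercise log "is a tool for personal use by the participant and will not be returned to the study team" (section 8.8).

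**Control arm.** Controls receive an assignment call and one mailing or email (sections 8.5 and 8.7). Both arms are then called at about 8-9 weeks to schedule the post-study visit (section 8.9).

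**Common assessment.** At about 10 weeks, and up to 14, both arms complete a post-study interview described as "a series of questionnaires to assess fall history and efficacy, substance use, prescription medications, physical and social environment, food security, and frailty", plus physical tests (section 8.9).

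**Reporting and analysis.** Under section 10 the Principal Investigator "will report all adverse events and Unanticipated Problems to the IRB". Section 11 has named staff monitor adverse events. Neither section says how events are to be found. Section 13 plans between-arm estimates for falls and physical function only.

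**The concern.** The plan sets a duty to report adverse events without a method for finding them. What staff learn about exercise harm depends mainly on whether an intervention participant attends a contact and raises the problem, or gives it in answer to a general prompt. A participant who is hurt and disengages is the case most easily lost.

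The two arms also differ greatly in opportunity to report. If adverse events are tabulated by arm, the table mixes true risk with the number of occasions on which someone could mention an event.

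Two uses of the pilot are at stake. First, it is meant to inform a large trial (section 3.2), and whether unsupervised exercise is tolerated in this population is part of that. Second, falls are a secondary outcome with a broad definition that includes hitting furniture (section 4.2.2), and the protocol does not specify recording whether a fall happened during an assigned exercise. A reader of the results could then not separate such falls from others.

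**Working it through.** The plan gives no adverse event rate, detection probability or safety precision, so there is no stated figure to reproduce. The check is a comparison of the text, followed by illustrations whose rates are all assumed.

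**1. Sources of harm information, side by side**

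| Source | Arm | Fixed injury or adverse event question specified? | Depends on |
|---|---|---|---|
| Voluntary mention (6.1) | Intervention | No | Attendance and disclosure |
| Group opening prompt and talk about falls (8.8) | Intervention | No; difficulty and falls | Attendance |
| Question on why exercise stopped (8.9) | Intervention | No; reasons for stopping | Call taking place |
| Home exercise log (8.8) | Intervention | Not available to staff | - |
| Post-study interview (8.9) | Both | None listed; fall history is | Completing follow-up |

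**2. Opportunity to report**
- Intervention: 10 group sessions + 10 calls = up to 20 contacts per participant.
- Control: none scheduled between the mailing and the scheduling call at about weeks 8-9.

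**3. Exposure at full uptake**
- 20 participants x 10 weeks x 3 per week = 600 bouts.
- 600 x 0.5 to 1.0 hours = 300 to 600 hours. The documents attach no harm rate to this.

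**4. Detection within the intervention arm (assumed rates)**
- Suppose two independent contacts in the week of an injury, with attendance *a* and disclosure *v*. Detection = 1 - (1 - *a* x *v*)^2.
- *a* = 0.5, *v* = 0.5: 1 - 0.75^2 = 44%.
- *a* = 0.9, *v* = 0.8: 1 - 0.28^2 = 92%.
- So 8% to 56% of injuries would go unreported across this range.
- With a true injury risk of 10% in 20 participants, the chance of at least one reported injury is 1 - 0.90^20 = 88% at full detection and 1 - 0.95^20 = 64% at 50% detection.

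**5. Comparability between arms, for adverse events of any kind (assumed rates)**
- Expected reports = n x risk x detection, with n = 20 and the same true risk of 20% in both arms.
- Detection 80% v 40%: 3.2 v 1.6 reports, apparent ratio 2.0.
- Detection 80% v 20%: 3.2 v 0.8 reports, apparent ratio 4.0.
- Equal detection: ratio 1.0.
- The ratio is simply one detection probability divided by the other. It shows the mechanism and does not estimate its size here.

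**6. Coverage of the common interview**
- Section 13 assumes 80% follow-up. If losses are equal by arm, 20 x 0.80 = 16 are interviewed and about 4 per arm are not.

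**7. What better ascertainment cannot cure**
- With perfect detection and 0 injuries in 20, the one-sided 95% upper bound is 1 - 0.05^(1/20) = 13.9%.

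**The case against.** The case on the other side has real force, and it rules out several stronger readings.

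- **A reader might infer that injuries surface only if volunteered.** The text does not support that. Therapists ask why exercise stopped, every group member gets an opening prompt, and falls are discussed weekly. What stands is that none of these is a fixed injury question and all depend on attendance in one arm.
- **A reader might infer that missed calls lead to no action.** Section 8.9 says only that no number of misses removes a participant, which is a retention rule. Section 6.1 provides for staff to contact participants using their tracking information. The protocol is silent on outreach after missed calls; silence is not a statement that staff do nothing.
- **A reader might infer that nothing records whether a fall happened during exercise.** The documents list questionnaire domains, not items, and the fall history form is not shown. It may ask this; the protocol does not specify it.
- **A reader might infer that a planned safety comparison is biased.** None is planned. Section 13's falls estimate can draw on a fall history taken from both arms at the same interview. Controls are assigned no exercises, so exercise injury itself is a single-arm question.
- **The pilot is small and declared minimal risk.** Even complete data would leave a wide upper bound, so size as well as ascertainment limits what it can say.

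The core gap remains: adverse events must be reported, and no method of eliciting them is specified in either arm.

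**Conclusion.** The concern holds in limited form. The protocol specifies no structured injury or adverse event question. Exercise harm reaches staff mainly through voluntary discussion and general prompts at contacts that can be missed and that only the intervention arm has, with no injury or adverse event domain listed at the one common assessment. Injuries may be missed, and any adverse event table by arm would not be a like-for-like comparison.

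The size is unknown. The unreported share of 8% to 56% and the apparent ratios of 2.0 to 4.0 rest wholly on assumed attendance, disclosure and detection. Two errors also run in opposite directions: more contact tends to raise intervention-arm counts, while misses within that arm make absolute harm look smaller. The documents therefore do not support saying that injuries will be missed by any given amount or that counts will be biased by a given ratio.

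No planned between-arm estimate uses these counts, and the primary outcomes are unaffected. The change is worth making because it is cheap and because tolerability is something the larger trial will need to know.

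**What to change.** 1. **Post-study interview, both arms.** Add the same short items: any injury; any medical care for a fall or injury; and, for each fall, whether it happened during exercise, unless the fall history form already asks this. Use this source for any by-arm description of harms. Report the number in each arm without a post-study interview, since about 20% are not expected to complete follow-up and may include those who disengaged.
2. **Weekly check-in, intervention arm.** Add one fixed, recorded injury/fall question to each existing call, for safety follow-up. List the answers separately as intervention-arm data, with the number of check-ins completed.

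I would not add outreach triggered by a run of missed contacts as a data-collection measure. It could prompt re-engagement and so alter session attendance, which is a primary outcome (section 4.2.1).

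**Cost.** A few items on existing forms and no new visits. The downsides are slightly longer interviews, recall over 10-14 weeks for the common source, and more recorded events to process.
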